## **9. STATISTICAL CONSIDERATIONS**

### **9.1 General Design Considerations**

This is an open label pilot study. The study will not include blinding given that this is a single group assignment to treatment. Study will not include a placebo or non-treatment group as this is a feasibility pilot study.

The sample size for this pilot study was selected to allow for a sufficient evaluation of the feasibility of carrying out the protocol across multiple NNDC centers given the available resources and provide preliminary data to motivate further study of this treatment approach.

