## STUDY SYNOPSIS

Title	A Pilot Study of iTBS in Bipolar I Depression
Source of Funding	Baszucki Brain Research Fund
Study Population	Participants aged 18+ years old with a diagnosis of bipolar I disorder, current episode depressed
Study Design	A multisite, open label pilot study to investigate the efficacy and safety of a novel accelerated intermittent theta-burst stimulation (iTBS) protocol while assessing for changes in neuroimaging biomarkers associated with treatment response
Primary Objectives	To examine the use of accelerated iTBS to treat symptoms of treatment resistant depression in bipolar I disorder and assess changes in neuroimaging biomarkers that may predict treatment response.
Number of Sites	2
Total number of Participants	10 (5 at each site)
Study Duration	1 year

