#### **Treatment Details:**

Motor threshold: Using single pulse TMS, the scalp position of lowest motor threshold for the left first dorsal interosseous or abductor pollicis brevis muscles will be determined. Resting motor threshold (MT) will be defined by the lowest power setting producing a visible muscle contraction in  $\geq 5$  of 10 trials.

rTMS system and treatment: For this study, we will be using the the MagVenture MagPro X100 rTMS Stimulator System (Magventure A/S, Denmark) equipped with a double-sided MagVenture Cool-B65 coil. A Localite neuronavigation system (Localite GmbH, Sankt Augustin, Germany) will be used to position the TMS coil over the individualized stimulation target at each session. All participants will receive stimulation using iTBS over the LDLPFC (1800 pulses per session). The individualized treatment targets will be produced from structural and functional MRI scans using the software services of Magnus Medical. The targeting approach will be the same as that used in prior publications (Cole et al., 2020, 2022; Williams et al., 2018).

Stimulation intensity will be standardized at 90% of left RMT, adjusted to skull to cortex distance. No further adjustments are needed based on other patient characteristics or conditions. For safety, stimulation will never be delivered above 120% rMT. Sessions will be delivered using the MagVenture MagPro X100 stimulator, with triple-pulse 50-Hz bursts given every 200ms (at 5 Hz).

The iTBS protocol will consist of a 2s train of bursts given every 10 s for a total of 570s (1800 pulses) over the LDLPFC.

If treatment emergent mania occurs (defined as an increase of 2 or more points in at least 2 YMRS items or clinician judgment), we will discontinue treatment and adjust anti-manic medication and, if necessary, add on other pharmacologic measures (neuroleptics, benzodiazepines) as clinically indicated with the intent to treat until remission is achieved.

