### **Neuroimaging Biomarkers:**

We will perform structural and resting state functional connectivity MRI with a 3T system prior to active study phase and immediately after active study phase (up to 5 days following final iTBS stimulation). The MRI scans will require about 1 hour in the MRI scanner. During the scan, participants will lie on the table in the magnet while the images are acquired. Instructions may be given through an auditory system. Subjects will wear earplugs and may be fitted for a bite bar to help them to keep their head still during the scans; for studies that enroll older adults, a bite bar will not be used so as to accommodate participants with dentures. These procedures have been used previously in younger and older adults alike, and do not cause undue distress in subjects.

At Baseline and 1 week, our MRI scans will include:

- Anatomical (T1) - 5min
- Resting state fMRI - 24 min
- Resting state ASL - 7 min

-Diffusion-weighted imaging (DWI) - DWI acquisition will take approximately 4 min along 90 non-collinear directions with a b-value=2400s/mm^2.

TOTAL scan time: ~40min

Biomarker measures: We will use a canonical hemodynamic response function (HRF) convolved event-related model with temporal and dispersion derivatives to model the blood oxygen level dependent (BOLD) in the context of a generalized linear model. Separate regressors (convolved with the HRF) will be created for stimulus events in each paradigm. Temporal and dispersion derivatives will be treated as regressors of no interest. A region of interest (ROI) analysis will be performed using our established methods, to identify BOLD-dependent signal change in the dorsolateral prefrontal cortex, subgenual cingulate, and default mode network nodes (right, left). Beta values for each ROI will be extracted for each subject for regression analyses.

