#### **9.3.2 Secondary Outcomes**

Secondary outcome measures will include changes in MRI derived functional connectivity of the subcallosal cingulate to the DLPFC and within the default mode network. Secondary outcome measures will be assessed as the change between baseline and 1-month post-treatment assessment. Exploratory endpoints include biometrics related to sympathetic nervous system activity - Heart Rate, Sweat Chloride, Body Temperature, and Actigraphy.

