## 9.4 Data Analyses

The primary outcome measures will be analyzed using generalized linear mixed models to test if there are significant changes in scores over follow-up. Based on previous work, we will use a compound symmetry or autoregressive covariance structure (based on distribution of residuals) and robust estimation of coefficients to handle violations of model assumptions. Random effects will be included to account for repeated measures on the same participants, and fixed effects of time will be evaluated controlling for fixed effects of age, sex and number of days to reach treatment remission. All post hoc pairwise comparisons will be Bonferroni corrected. Exploratory endpoints related to biometrics will be analyzed in similar fashion.

For assessment of the secondary outcome measures of change in functional connectivity, we will employ a resting-state seed-based functional connectivity approach to assess connectivity between the subcallosal cingulate connectivity to the DLPFC and within the default mode network. For each participant, the correlation coefficients between average blood oxygen level-dependent (BOLD) time series of the seed-region and the BOLD time series of each grey matter voxel within the DLPFC or default mode network will be calculated. The correlation coefficient will be converted to normally distributed z scores by the application of Fisher's r to z transformation. The resulting connectivity maps will be analyzed with repeated measures ANOVA to compare pre-iTBS vs post-iTBS connectivity measures as a within-subject variable, and sex and site as a between-subject covariate.

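### The reason given for having no blinding does not cover the pre/post scan comparison, and the plan has neither masked scan processing nor a scan-exclusion rule, so a possible bias in the secondary outcome is uncontrolled

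*Combined protocol and SAP*

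**What the plan says.** Section 9.1 describes an open-label, single-group pilot and says: "The study will not include blinding given that this is a single group assignment to treatment". Section 10.1 (Data Collection) repeats the sentence. Neither section makes an exception for any outcome or any stage of data handling.

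On the imaging outcome, section 9.3.2 says: "Secondary outcome measures will include changes in MRI derived functional connectivity of the subcallosal cingulate to the DLPFC and within the default mode network". Section 9.4 gives the contrast: "The resulting connectivity maps will be analyzed with repeated measures ANOVA to compare pre-iTBS vs post-iTBS connectivity measures as a within-subject variable", with sex and site as between-subject terms. The Neuroimaging Biomarkers part of section 5.1 and the schedule in section 6.1 provide two MRI sessions per participant, one before treatment and one within days of its end.

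On processing, the Neuroimaging Biomarkers text says: "A region of interest (ROI) analysis will be performed using our established methods". Section 9.4 adds a seed-based correlation approach with Fisher's transformation. Neither place says who processes the outcome scans, what that person knows, how the seed and masks are defined, or when a scan is too poor to use.

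The baseline scan has a second use, in section 5.1 (Treatment Details): "The individualized treatment targets will be produced from structural and functional MRI scans using the software services of Magnus Medical".

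**The concern.** Single-group assignment explains why treatment cannot be masked. It has no bearing on whether time point can be masked. In the connectivity analysis, time point is the factor under test, and it can be hidden from the people who pre-process, quality-check and extract the data. So can each participant's MADRS result.

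Connectivity change is the only named secondary outcome. Biomarker change is also part of the primary objective in section 1.1, and the abstract says the pilot is meant to lead to a larger study of the treatment and of factors associated with response. With no control arm, nothing in the data would show whether an apparent change came from handling choices. With at most 10 pairs, one choice about one scan carries weight.

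**Working it through.** **Step 1: does the stated reason reach the imaging step?**

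- Sections 9.1 and 10.1: no blinding, because there is one treatment group.
- Section 9.4: the comparison is pre-iTBS against post-iTBS within each participant.
- Having one group removes allocation as something to mask. It leaves scan order and MADRS response, both of which can be masked. The reason therefore does not extend to this analysis.

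**Step 2: does anything else in the plan control the bias?**

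A fully fixed pipeline would do much of the work of masking. The plan names the regions and the correlation method, but gives no seed coordinates, mask source, motion limit or exclusion rule. The two descriptions of the analysis also differ. The Neuroimaging Biomarkers text describes an event-related model with stimulus regressors, while section 9.4 describes resting-state seed correlation. Some analytic choices therefore remain open.

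**Step 3: how large could the effect be?**

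The plan gives no figure to reproduce. Section 9.1 rests the sample size on feasibility ("The sample size for this pilot study was selected to allow for a sufficient evaluation of the feasibility of carrying out the protocol") and on available resources, and states no alpha, power, effect size or standard deviation. What follows is an illustration under assumptions.

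Inputs:

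- From the synopsis: 2 sites × 5 participants = 10 pairs at most, hence 10 × 2 = 20 sessions.
- Assumed: no true change; independent, standard normal within-person differences d; paired t-test; two-sided alpha 0.05.

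Formula: t = mean(d) / (SD(d)/√k), where k is the number of pairs kept. The critical value is 2.262 for k = 10 (9 df) and 2.306 for k = 9 (8 df). Rates are from simulation.

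For the partial case, each pair has a quality score c = ρd + √(1 − ρ²)e, with e independent standard normal, and the pair with the lowest c is dropped. The correlation ρ measures how far the exclusion criterion tracks the connectivity difference. The plan gives no basis for choosing ρ, so a range is shown.

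| How one pair is dropped | False positives, favoured direction | Two-sided |
|---|---|---|
| None dropped | 2.5% | 5.0% |
| Unrelated to the difference | about 2.5% | about 5% |
| ρ = 0.1 | about 2.8% | about 5% |
| ρ = 0.2 | about 3.1% | about 5% |
| ρ = 0.3 | about 3.5% | about 5% |
| ρ = 0.5 | about 4.4% | about 6% |
| Always the most opposed pair (upper bound) | 8.8% | – |
| Full sample, or drop the pair opposing whichever direction is favoured (upper bound) | – | about 17.5% |

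The last two rows require the connectivity difference itself to be known when the pair is dropped. Knowing scan order or MADRS response during quality control is a weaker condition, and the rows for ρ between 0.1 and 0.5 are nearer to it.

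**The case against.** **The sentence is about treatment.** In section 9.1 it stands between the open-label statement and the explanation for having no placebo or untreated group. In section 10.1 it closes a paragraph on site staff collecting data. This stands: the natural reading is treatment masking, and the plan should not be described as deliberately forbidding masked image analysis. But the sentence is unqualified, and masked processing is not provided for elsewhere.

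**A reader might infer that scans will be processed and excluded by people who know scan order and response.** The documents do not support that. They identify no image analyst, do not say who sees dates or MADRS scores, and describe no scan exclusion.

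**The analysis may be largely automatic.** Section 9.4 sets out a computed sequence with regions named beforehand, and nothing says that seeds or masks are placed by hand. This is fair, and a scripted pipeline with fixed thresholds would leave less room for bias. The plan does not commit to one. The point also shows that masking alone is not enough: masked analysts without a threshold would still exclude by discretion.

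**The large figures overstate the problem.** This stands. A reader might take 8.8% or 17.5% as the expected inflation, but they describe deletion driven by the result. An unmasked analyst whose exclusions are unrelated to the difference keeps the nominal rate.

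**It is a secondary outcome in a 10-person pilot.** True, and no decision threshold is attached to imaging. That limits the weight of the point but does not remove the case for an inexpensive safeguard.

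**Conclusion.** The point holds as a gap in bias control. The reason given for no blinding does not apply to the pre/post connectivity comparison, and the plan has neither masked processing nor a prespecified scan quality or exclusion rule. Bias from knowing scan order or MADRS response is therefore possible and uncontrolled, but not documented.

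Under the assumptions above, the plausible effect of one exclusion is modest: 2.5% rising to about 2.8% to 4.4% in the favoured direction for ρ from 0.1 to 0.5. The upper bounds are 8.8% in one direction and about 17.5% in either. These figures come from a plain paired t-test; the planned repeated measures ANOVA on connectivity maps, with sex and site, was not modelled. This is a worthwhile, inexpensive improvement to a secondary outcome, not a flaw that undermines the study.

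A separate matter affects the same outcome: section 9.3.2 times secondary change at one month, but section 6.1 schedules no MRI then. Those sections need reconciling in any case.

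**What to change.** In sections 9.1 and 10.1, limit the sentence to treatment: *Treatment is not blinded.*

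Add to section 9.4:

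- *Outcome scans are given random session codes, with dates removed, by a study team member who does not carry out the image analysis.*
- *Seed and mask definitions and a motion/quality exclusion threshold are fixed before any outcome scan is processed.*
- *Pre-processing, quality control and exclusions are completed and logged before scan order and MADRS results are disclosed to the analysts.*

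The second item is needed because masking does not by itself prevent discretionary exclusion. The threshold is for the imaging team to choose and state.

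Target generation from the baseline scan is a separate, earlier step and is unaffected. No visit, treatment or clinical rule changes.

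The cost is recoding and logging at most 20 sessions, with one existing team member holding the code list. Section 10.2 describes coded IDs only for REDCap data and does not cover scan storage, so the code holder and the place where the list is kept should be named. The coordinating centre is also a treating site, so that person should be chosen with the separation from image analysis in mind.

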### **9.2 Early Stopping Rules**

The study will be terminated if:

Three or more participants reach hypomania as defined by a score of greater than 10 on the YMRS scale without resolution (YMRS <10) within 24 hours with pharmacologic measures as outlined above.

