## 4. SELECTION AND ENROLLMENT OF PARTICIPANTS

### 4.1 Inclusion Criteria

1. 18+ years of age
2. Bipolar I disorder diagnosis as defined by The Diagnostic and Statistical Manual of Mental Disorders, Fifth Edition (DSM-5)
3. Currently experiencing a Major Depressive Episode with Montgomery-Asberg Depression Rating Scale (MADRS)  $\geq 20$  at screening [Day -5/-14] and baseline [Day 0]
4. On a stable and adequate dose of an anti-manic agent (Lithium with a level of at least 0.6, Depakote with a level of at least 50, or a therapeutic dose of carbamazepine, oxcarbazepine, or a neuroleptic for treatment of mania per clinician judgment) without dose changes for at least 6 weeks prior to the active study time period. Final assessment of appropriateness of participant's pharmacologic regimen is subject to study team clinician judgment.
5. Having failed a therapeutic trial of a first line bipolar depression antidepressant (as specified by the Antidepressant Treatment History Form and updated with new medications approved by the FDA for treatment of bipolar depression) in this current episode. This includes a minimum 4 week trial of one of the following medications (minimum dosage): lithium 900mg daily (or blood level  $\geq 0.6$  mEq/L), carbamazepine 400mg daily (or blood level  $\geq 0.8$  mEq/L), lamotrigine 200mg daily, asenapine 20mg daily, lurasidone 20mg daily, olanzapine 10mg daily, quetiapine 300mg daily, or lumateperone 42mg daily. Final determination of a failed adequate therapeutic trial is subject to study team clinician judgement.
6. Established outpatient psychiatrist

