### 4.2 Exclusion Criteria

1. Female that is pregnant or breastfeeding, or of childbearing potential but not using medically acceptable birth control during study
2. Current mixed episode assessed by clinician judgment as defined by DSM-5 criteria
3. Current active substance use disorder (as defined by DSM-5) with exception of nicotine and caffeine. Participants may be subject to urine drug screen base on study team clinician judgment.

4. Participation in any clinical trial with an investigational drug or device within the last 3 month or concurrent to study participation
5. History of epilepsy, shrapnel or metal in the head or skull, cardiovascular disease/event, OCD, or autism spectrum disorder
6. Clinically defined major neurological disorder; including, but not limited to, seizure disorder and history of loss of consciousness due to head injury for greater than 10 minutes, or documented evidence of brain injury
7. Active suicidal risk based on investigator's clinical judgment
8. Clinically significant unstable medical condition
9. Other condition judged by investigator that could prevent the participant from completion of the study (such as but not limited to, significant physical disability (e.g., hearing/visual deficits) to perform a neutral memory task and/or neuropsychological test battery)
10. Ferromagnetic metal implant or another contraindication to imaging in a 3 Tesla MRI
11. ECT treatment in the past 3 months
12. Minimum of 6 months since last manic or hypomanic episode as defined by DSM-5 criteria

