## 6.2 Descriptions of Evaluations

### **Screening [Day -5/-50]:**

We will recruit participants from our clinics with a treatment history verifying they meet inclusion/exclusion criteria (see below in Section 5). We will obtain informed consent from the participant and a trained rater will administer a SCID (Structured Clinical Interview for DSM-5) to confirm the diagnosis of bipolar I disorder. Participants will be staged using a modified Maudsley staging method tailored for bipolar depression to determine the severity of treatment resistance. The consenting and clinical screening assessment will be performed in-person, or virtually by secure audio/video platform as works best for the individual and current COVID environment. We will also gather the participants' medical records and review all information to screen for inclusion and exclusion criteria, MRI safety, TMS safety, medical and psychiatric history, a pregnancy test, and current medications.

At the clinical screening assessment, a trained rater will also collect the following assessments:

1. MADRS (Montgomery-Asberg Depression Rating Scale)
2. YMRS (Young Mania Rating Scale)
3. CGI-BP (Clinical Global Impression – Bipolar Disorder)
4. ATHF current and lifetime (Antidepressant Treatment History Form) – ATHF reviews patient antidepressant trials to assess whether patients have had “failed, adequate trials” of various classes of antidepressants.
5. TASS (Transcranial Magnetic Simulation Adult Safety Screen) – a screening form that evaluates prior adverse reaction to TMS and various seizure risk factors and relative contraindications

Participants will also complete the following:

1. AS-18 (Affective Self Rating Scale)
2. PANAS (Positive and Negative Affect Schedule)
3. digiBP (Digital Self-Report Survey of Mood for Bipolar Disorder)
4. MADRS-S (Montgomery-Asberg Depression Rating Scale – Self Rated)
5. C-SSRS (Columbia Suicide Severity Rating Scale)

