### **6.3 Description of Study Measures**

- a. Montgomery-Asberg Depression Scale-Clinician Rated (MADRS): The MADRS is a ten-item clinician rated questionnaire. Total scores can range from 0 to 60, with higher scores indicating greater severity of depression (0-6 normal range, 7-19 mild depression, 20-34 moderate depression, >34 severe depression). We will utilize this assessment to determine participant's level of depression and consequent eligibility for the trial. We will then subsequently utilize the MADRS daily and at follow up as our primary outcome measure.
- b. Young Mania Rating Scale (YMRS): The YMRS is an 11-item clinician-administered scale used to measure symptoms of mania. Each item is scored from 0-4 with scores of 4 indicating the presence of more severe mania. This scale will be used to monitor symptoms of mania through each day of iTBS treatment.
- c. Clinical Global Impression Scale - Bipolar Disorder (CGI-BP): The CGI-BP is a 3-item clinician rated scale to provide a global rating of severity of manic and depressive

episodes and the degree of change from the immediately preceding phase and from the worst phase of illness. Each item is rated from 1 to 7 (0 = not assessed and 7 = very much worse or severely ill). The CGI-BP will be administered at screening, baseline and visit follow ups for a more global assessment of patient's illness and symptoms.

- d. Affective Self Rating Scale (AS-18): The AS-18 is a 18 item self-rating scale that assess depressive, manic, and mixed affective states. Each symptom is rated from 0 "none" to 4 "very severe". The AS-18 will be filled out at every study encounter: screening, baseline, active study, and follow up.
- e. Positive and Negative Affect Schedule (PANAS): The PANAS is a 20-item self report scale that consists of different words that describe different positive and negative feelings and emotions. Every item is rated from 1 "very slightly or not at all" to 5 "extremely". The PANAS will be filled out screening, baseline, and follow up encounters. A modified PANAS (items 3, 9, 11, 17, 18, 19) will be administered between every stimulation session to assess for any potential shift towards (hypo)mania

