## 7. SAFETY ASSESSMENTS

### **Risk Assessment:**

**TMS:** Extensive published data show that this accelerated theta-burst rTMS protocol in prefrontal cortex is safe and very well tolerated (Sonmez et al., 2019). The most common side effects were mild headache, fatigue, and some discomfort at the stimulation site.

No seizures were observed in any of the above studies. However, very rarely, TMS can induce seizures (17 reported cases to date among tens of thousands of participants treated with rTMS, but few to none if proper safety and enrollment procedures are followed), with a seizure risk at approximately 1:30,000 sessions for traditional high frequency rTMS (Rossi et al., 2009). To minimize the chances of this adverse event, participants with seizure history will be excluded. The FDA has considered studies of standard TMS to be nonsignificant risk (not requiring an IDE).

Another potential immediate risk is that of induction of mania. Although there have been no such cases of mania induced by TBS, there have been at least 13 cases of rTMS-induced mania reported from fixed-frequency rTMS in participants with depression (Xia et al., 2008). The rTMS-induced mania rate reported by Xia et al was 0.84% as compared to 0.73% for sham, which were not significantly different from each other.

Another potential risk is mild pain at the site of stimulation, which occurs during stimulation only, and which wanes with each session. There is also a risk of psychological distress related to this pain, should it occur, though discomfort associated with rTMS is typically mild, and not distressing when participants are reassured it is not dangerous. For participants that continue to experience discomfort with TMS, pre-treatment with acetaminophen, ibuprofen, and/or lidocaine will be allowed as warranted. Participants and treaters will wear earplugs during all treatment sessions. In between sessions, participants will be placed in a relaxing environment to maximize psychological well-being.

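### The stopping rule in Section 9.2 sets hypomania at YMRS above 10 and resolution at YMRS below 10, but Section 4 sets no YMRS entry limit, so a permitted entrant can worsen, return to the Day 0 score and still count as unresolved.

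*Combined protocol and SAP*

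**What the plan says.** Section 9.2 holds the only study-level stopping rule. The study ends if "Three or more participants reach hypomania as defined by a score of greater than 10 on the YMRS scale without resolution (YMRS <10", with the time allowed and the treatment given as "within 24 hours with pharmacologic measures as outlined above". Neither cut-off refers to the participant's own baseline.

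Section 4.1, item 3, sets a numeric limit for depression: "Currently experiencing a Major Depressive Episode with Montgomery-Asberg Depression Rating Scale (MADRS" at least 20, required at screening and again at Day 0. For manic symptoms, Section 4.2 has two clinical criteria and no score: item 2, "Current mixed episode assessed by clinician judgment as defined by DSM-5 criteria", and item 12, "Minimum of 6 months since last manic or hypomanic episode as defined by DSM-5 criteria" (listed as an exclusion but plainly meant as a requirement). Section 4.1, item 4, also requires a stable anti-manic agent.

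The YMRS is rated at screening ("YMRS (Young Mania Rating Scale" in the Section 6.2 list) and again among the Day 0 clinical measures. Sections 6.1 and 6.2 let screening fall up to 50 days before Day 0. Section 6.3 describes 11 items: "Each item is scored from 0-4 with scores of 4 indicating the presence of more severe mania".

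The rule for stopping an individual's treatment (Sections 5.1, 6.2, 7.1 and 7.2) works differently. It depends on change: two YMRS items each up by two points or more. Sections 5.1, 6.2 and 7.2 also allow clinician judgment.

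**The concern.** The protocol uses a YMRS score to decide who has become hypomanic and who has recovered, but not to decide who may enter. Nothing numeric keeps out a person who is already at or above the score that 9.2 calls hypomania. If that person worsens under stimulation and then goes fully back to the Day 0 score, 9.2 still treats the episode as unresolved, because the Day 0 score is not below 10.

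Two things are at stake. One is safety at entry: someone in the protocol's own hypomania range could receive up to 50 sessions. The other is consistency of the count: an episode that has reversed would use one of the three counts that end a ten-person study.

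**Working it through.** The plan gives no operating characteristics for 9.2, so there is no figure to reproduce. The check has two parts.

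**1. The rule applied to single participants.** The smallest change that meets the individual trigger, with all other items unchanged, is 2 items x 2 points = 4 points.

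- Entry 12: 12 + 4 = 16, above 10. Treated and back to 12 within 24 hours: 12 is not below 10, so unresolved. Resolution needs a score of 9, which is 12 - 9 = 3 points below entry.
- Entry 10: 10 + 4 = 14, back to 10: not below 10, unresolved. Resolution needs 1 point below entry.
- Entry 9: 9 + 4 = 13, back to 9: below 10, resolved.

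The mismatch therefore arises only for entry scores of 10 or more.

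**2. How often it could matter.** Inputs:

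- n = 10 participants and a stop at 3 (Synopsis; Section 9.2).
- p, the share entering above 10: not in the documents; assumed 1-5%.
- w, the share of those who worsen and return to the Day 0 score: not in the documents. The low end is 0.84%, borrowed from the rTMS mania rate in Section 7, which "was 0.84% as compared to 0.73% for sham" and comes from another population. 10% and 50% are assumed, and 50% is deliberately extreme.
- q, the rate of genuine unresolved events: 0.84% (same source), 5% and 10% (both assumed).

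Participants are taken as independent.

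At least one entrant above 10, 1 - (1 - p)^10: 9.6% at p = 1%, 18% at 2%, 26% at 3%, 40% at 5%.

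At least one disputed count, 1 - (1 - pw)^10:

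| | w = 0.84% | w = 10% | w = 50% |
|---|---|---|---|
| p = 1% | 0.08% | 1.0% | 4.9% |
| p = 5% | 0.42% | 4.9% | 22% |

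These are chances of one disputed count, not of a stop. For the stop, compare P(X >= 3) for X ~ Binomial(10, q + pw) with the same probability at q alone:

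| q | Stop probability at q alone | Increase, p = 1%, w = 0.84% | Increase, p = 5%, w = 10% | Increase, p = 5%, w = 50% |
|---|---|---|---|---|
| 0.84% | 0.0068% | 0.0002 points | 0.020 points | 0.37 points |
| 5% | 1.15% | 0.005 points | 0.34 points | 2.2 points |
| 10% | 7.0% | 0.014 points | 0.89 points | 4.9 points |

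If one such count has already occurred, two more among the other nine end the study. That conditional probability is 7.1% at q = 5% (against 1.15% unconditionally) and 23% at q = 10% (against 7.0%).

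Entrants at exactly 10 are not in p and would add somewhat to these figures.

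**The case against.** The strongest reply is that an absolute resolution score is a sound safety choice. The participant in question has bipolar I disorder, worsened under stimulation, was given anti-manic treatment, and a day later still scores at or above 10. Declining to call that resolved is cautious. The possible error is an early stop of an open-label pilot, not missed harm, and the change-based individual rule protects each participant whatever 9.2 says. This stands, and it is why 9.2 itself should not be loosened. Moving resolution to 10 or below, for example, would relax the only study-level safety rule for everyone in order to correct a rare case.

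It is also true that entry is controlled clinically. The mixed-episode and six-month criteria, the required anti-manic agent, the separate baseline visit to check that symptoms are stable, and the team's eligibility review (Section 10.3.3) all make a high entry score uncommon. None of them sets a number.

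A reader might infer three stronger things that the documents do not support:

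- That participants who enter high and stay flat would stop the study. The verb in 9.2 and its reference to treatment already described point to treatment-emergent events. Even if flat entrants counted, three or more of ten would occur with probability 0.01% at p = 1% and 1.2% at p = 5%.
- That a score of exactly 10 is a gap in the rule. It is not: after a score above 10, a 10 is unresolved, and the rule can be applied as written.
- That the two sites would count differently. Section 13.1 sends protocol events to both the site and the lead investigator at the same time, which limits this.

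**Conclusion.** The point holds as a minor one. On the text alone, an entrant at 10 or above can be stimulated and cannot count as resolved by returning to the Day 0 score. Across the assumed ranges for p and w, the effect on the stopping probability is 0.0002 to 0.37 percentage points at a 0.84% event rate. It approaches 5 points only if p = 5%, w = 50% and q = 10% all hold. The direction is towards stopping sooner.

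That high entry is uncommon is an inference from the eligibility criteria; the documents give no baseline YMRS distribution. The values of p and w, and the higher values of q, are assumptions. The case for acting rests less on the stopping probability than on entry safety and on using the same score consistently at entry and in 9.2.

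**What to change.** Add to Section 4 a requirement of YMRS below 10 at screening and at Day 0, and leave 9.2 unchanged. Every permitted Day 0 score is then 9 or lower, so every return to it counts as resolved, and nobody in the protocol's hypomania range at Day 0 is stimulated. The Day 0 check matters because screening may be up to 50 days earlier.

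The change is one eligibility line and uses ratings already collected. It screens out a few otherwise eligible people: 10 x 0.01 = 0.1 to 10 x 0.05 = 0.5 per 10 at the assumed 1-5% above 10, and slightly more once those at exactly 10 are included. A failure at Day 0 comes late, but the MADRS limit already carries that cost at the same visit.
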